#### 11.4.3 Pharmacokinetic Endpoints

Blood samples for PK assessments will only be collected for subjects in Part 2 (Cohorts 4 and 5 expansion groups) of the study. Pharmacokinetic endpoints of this study are to characterize the plasma PK parameters of VP-315 and its metabolites following multiple doses of VP-315; standard noncompartmental methods will be used.

#### 11.4.4 Exploratory Endpoints

Tumor tissue samples from the pre-treatment screening biopsies and from the post-treatment excised tumor tissue will undergo multiplexed IF-IHC and changes in the expression of a panel of 8 immune markers in response to the treatment will be analyzed. Additionally, genomic DNA will be isolated from the same tissue samples, as well as from peripheral blood samples collected at the same pre- and post-treatment time points and will undergo sequencing and analyzed for changes in T-cell receptor clonality.

#### 11.5 Analysis Methods

### 11.5.1 Subject Characteristics and Disposition

Descriptive summaries of demographic and baseline characteristics for all enrolled subjects will be tabulated by study part. The number of subjects included in each analysis population will be summarized, along with the reason for exclusion from any analysis populations. Subjects discontinuing from study drug or withdrawing from the study and the primary reason for discontinuation/withdrawal will be summarized.

# 11.5.2 Safety Analyses

All subjects who receive any amount of study drug will be included in the safety analysis. Safety will be evaluated by study part.

All AEs will be coded using the MedDRA dictionary. Tabular summaries of AEs will only consider treatment-emergent adverse events (TEAEs), which are defined as those AEs with a start date on or after first dose of study drug. The incidence of TEAEs will be summarized by system organ class (SOC), preferred term (PT), relationship to study drug, and severity. Serious TEAEs will be summarized by SOC and PT. TEAEs leading to discontinuation as well as TEAEs identified as dose limiting toxicities will be listed and summarized if sufficient counts of either are reported.

Hematology and serum chemistries will be summarized using conventional summary statistics (mean, standard deviation, median, and range). In addition, a change from baseline will be presented. Standard shift tables will also be prepared presenting toxicity grade vs baseline.

Vital signs and ECG results will be summarized in a descriptive manner by calculating the mean, standard deviation, median, and range in the same manner described for laboratory values. Change from baseline for vital signs and ECG parameters will also be summarized. For ECG parameters, both QTcB (Bazett's correction) and QTcF (Fridericia's correction) will be displayed.

Cutaneous Reaction Assessments will be summarized using counts and percentages for each severity level (none, mild, moderate, severe). Separate summaries will be presented for each cutaneous reaction type and visit.

#### 11.5.3 Efficacy Analyses

Efficacy analyses will be conducted for all lesions of all subjects enrolled in the study and carried out by study part.

Complete clearance will be summarized using counts and percentages. Histological clearance and clinical clearance will be summarized using similar methods. Other efficacy endpoints to be summarized include estimates of tumor volume, abscopal effect on nontreated lesions, PGA, SCAR-Q (Part 2 and 3 only) and FACE-Q (Part 2 and 3 only). Each endpoint will be summarized as described in Section 11.1, based on the type of data collected.

#### 11.5.4 Pharmacokinetic Analyses

Blood samples will be collected on the first day of dose administration immediately prior to the VP-315 dose and at 2-and 5-minutes post first injection, and 2-, 5-, 10-, 20-, 30-, 60-, and 120-minutes post last injection. Additional samples will we collected at 24 ( $\pm 1$ ) hours post-dose prior to administration of the next VP-315 dose. Blood samples for PK will only be collected for subjects in Part2 (Cohorts 4 and 5 expansion groups) of the study.

Concentrations of VP-315 and metabolites will be determined in plasma using a validated bioanalytical assay(s). Individual subject VP-315 concentration-time data will be displayed using scheduled sampling times. Descriptive statistics (e.g., n, mean, SD, %CV, median and range) will be calculated for each sampling time. Plasma concentrations of the study drug over time will be plotted in semilogarithmic and linear formats as mean  $\pm$  SD. Plasma concentration-time data for each subject will be analyzed using standard noncompartmental methods. Plasma PK parameters of VP-315 and metabolites will include  $C_{max}$ ,  $T_{max}$ ,  $AUC_{0-last}$ , and  $AUC_{inf}$ .

Dose proportionality information will be obtained by comparing plasma levels of VP-315 across all dose levels. The primary method for evaluation of dose proportionality will be based on  $AUC_{0\text{-last}}$ ,  $AUC_{inf}$ ,  $AUC_{tau}$ , and  $C_{max}$ . The population mean slope will be estimated with a 90% CI. An alternate evaluation of dose proportionality will be conducted using ANOVA on dose-normalized  $AUC_{0\text{-last}}$ ,  $AUC_{inf}$ , and  $C_{max}$ . The analysis will be conducted on log-transformed data. The model will include dose as a fixed effect and subject as random effect. Calculations of the 90% CI for the ratio of dose comparisons will be constructed.

Descriptive statistics for VP-315 PK concentrations will be tabulated at each scheduled timepoint by cohort. Statistics for PK concentrations will include the number of subjects, mean, standard deviation, CV%, median, minimum, maximum, geometric mean, and geometric CV%.

Descriptive statistics for VP-315 PK parameters will be provided for Cohorts 4 and 5 expansion subjects in Part 2. Summaries will include the number of subjects, mean, standard deviation, CV%, median, minimum, maximum, geometric mean, and geometric CV% (where applicable).

#### 12. ETHICAL, LEGAL AND ADMINISTRATIVE ASPECTS

#### 12.1 Ethical Conduct of the Study

The procedures set out in this protocol, pertaining to the conduct, evaluation, and documentation of this study, are designed to ensure that the Sponsor, its authorized representative, and investigators abide by Good Clinical Practice (GCP) as described in International Council for Harmonisation (ICH) guideline E6(R2), and in 21 CFR parts 11, 50, 54, 56, and 312. Compliance with these regulations also constitutes compliance with the ethical principles described in the most recent revision of the Declaration of Helsinki (October 2013) that is recognized by the US Food and Drug Administration (FDA), the European Medicines Agency, and other regulatory agencies.

#### 12.2 Informed Consent

A template ICF will be provided by the Sponsor or designee. According to the Protection of Human Subjects regulations listing in 21 CFR Part 50, the ICF must be reviewed and approved by the IRB and must contain all elements required, as applicable, by national or local laws/regulations or requirements, US FDA regulations or regulations of the authority having jurisdiction over the location in which the study is being conducted, and institutional policies. If, during the approval process, the IRB makes any substantive changes to the ICF, then this altered ICF must be provided to the Sponsor or designee for review before it is implemented.

All subjects will be provided with the approved written ICF for this study, which will provide sufficient information for the subject to make an informed decision about participation in this study and to facilitate comprehension of the information. Each subject will be provided adequate opportunity to ask questions and to consider whether to participate. The investigator is responsible for obtaining the potential subject's voluntary agreement to participate, and to continue providing information as the clinical study progresses or as the subject or situation requires.

Voluntary informed consent must be obtained from each eligible subject before any protocoldefined procedures are performed. The subject's signature on the ICF indicates his/her willingness to participate in this study. Other study personnel (e.g., Principal Investigator, Study Nurse) will sign the ICF in accordance with local procedures.

#### 12.3 Institutional Review Board

A copy of the protocol, proposed ICF, other written subject information, and any proposed advertising material must be submitted to the IRB for written approval. A copy of the written approval of the protocol and ICF must be received by Sponsor before recruitment of subjects into the study and shipment of VP-315.

The investigator must submit and, where necessary, obtain approval from the IRB for all subsequent protocol amendments and changes to the ICF. The investigator is to notify the IRB of deviations from the protocol or SAEs occurring at the site and other AE reports received from Sponsor, in accordance with local procedures.

13 October 2023

The investigator is responsible for obtaining annual IRB approval/renewal throughout the duration of the study. Copies of the investigator's reports and the IRB continuance of approval must be sent to Sponsor.

# 12.4 Subject Confidentiality

All information generated in this study is considered highly confidential and must not be disclosed to any person or entity not directly involved with the study unless prior written consent is gained from the Sponsor. However, authorized regulatory officials, IRB personnel, the sponsor and its authorized representatives are allowed full access to the records.

All study subjects must be informed that their personal study-related data will be used by the Sponsor in accordance with local data protection laws. The types of disclosure must also be explained to the subject, who will be required to be informed about how their data will be used as described in the ICF. The subjects must be informed that their medical records may be examined by auditors or other authorized personnel appointed by the Sponsor, by appropriate IRB members, and by inspectors from regulatory authorities.

Identification of subjects and eCRFs shall be by unique subject identification numbers (such as screening number) only. All personal identifiers according to applicable regulations (e.g., name, phone number) must be redacted permanently by the site personnel and replaced with the subject's unique identification number in all records and data before transfer to the Sponsor (or designee).

All personal details will be treated as confidential by the investigator and staff.

# 12.5 Investigator Signatory Obligations

The investigator is to sign each clinical study report.

#### 13. ADMINISTRATIVE AND LEGAL OBLIGATIONS

#### 13.1 Protocol Amendments and Study Termination

Protocol amendments, except when necessary to eliminate an immediate hazard to subjects, must be made only with the prior approval of the Sponsor. Agreement from the investigator must be obtained for all protocol amendments and amendments to the ICF. The IRB must be informed of all amendments and give approval prior to their implementation. The Sponsor will submit any study protocol amendments to the concerned regulatory authorities for approval and keep the investigator updated as detailed in the ICH GCP guidelines. The amendment must be signed by the investigator and approved prior to implementation, except if amendments are issued to eliminate an immediate hazard(s); in such case the amendment may be retrospectively approved. The investigator should not implement a change to the protocol without prior review and documented approval/favorable opinion of the IRB of an amendment, except where to eliminate an immediate hazard(s) to the study subjects.

Where only administrative changes are required to the protocol, the IRB will be notified for informational purposes only.

Sponsor reserves the right to terminate the study at any time. Both Sponsor and the investigator reserve the right to terminate the investigator's participation in the study according to the study contract. The investigator is to notify the IRB in writing of the study's completion or early termination (ET) and send a copy of the notification to Sponsor.

#### 13.2 Study Documentation and Archive

The Principal Investigator shall retain all study-related documentation, including source data, source documents, eCRFs, laboratory and diagnostic results, protocol and amendments, study drug accountability records, regulatory documentation and correspondence, ICFs, patient identification lists, and correspondence. These records should be retained in the format they were originally obtained (e.g., electronic or paper) unless a quality controlled and authorized complete electronic version is created for long-term storage at the end of the study. The Sponsor will provide an electronic copy of the final eCRF for each study subject within 3 months of study closeout.

The investigator must retain an organized file with all study-related documentation that is suitable for inspection by the Sponsor and representatives of Regulatory Authorities.

The investigator shall retain all study records for the longer of 1) 2 years after the last marketing authorization for the investigational product has been approved or Sponsor has discontinued research on the investigational product, and 2) such longer period as required by regulatory requirements.

Documents should be stored in such a way that they can be accessed, and data can be retrieved at a later date. Consideration should be given to security and environmental risks.

Documentation retention will generally comply with Section 8 of the ICH consolidated guideline on GCP, Essential Documents for the Conduct of a Clinical Trial.

No study document will be destroyed without prior written agreement between the Sponsor and the investigator, or the Research Site should the investigator leave the institution. Should the investigator wish to assign the study records to another party or move them to another location, written agreement must be obtained from the Sponsor prior to any actions being taken.

# 13.3 Study Monitoring and Data Collection

Clinical research associates (CRAs) representing the Sponsor will routinely visit the study site or develop a remote monitoring strategy throughout the study. The investigator will ensure that the monitor, or other compliance or quality assurance reviewer, is given access to all study-related documents and study related facilities (e.g., pharmacy, diagnostic laboratory, medical records), and, if the visit occurs on site, has adequate space to conduct the monitoring visit. In addition to the monitoring visits, frequent communications (email, letter, telephone, and/or fax) by the CRA will ensure that the investigation is conducted according to protocol design and regulatory requirements. The investigator, or appropriate designee, will allocate adequate time for monitoring activities and F/U correspondences.

The CRA will review ICFs, eCRFs, and laboratory and other diagnostic reports, comparing them with source documents to verify adherence to the protocol, and to ensure complete, accurate, consistent, and timely collection of data. The CRA will record and report any protocol deviations not previously sent to the Sponsor. The CRA will also confirm that AEs and SAEs have been properly documented on eCRFs and confirm that any SAEs have been forwarded to the Sponsor and those SAEs that met criteria for reporting have been forwarded to the IRB. The investigator will be asked to provide any missing information or to clarify any discrepancies found by the CRA. For on-site monitoring visits, it is expected that the investigator will be present for a concluding review at the end of each monitoring visit. Remote monitoring may be done if feasible, per the Monitoring Plan.

#### 13.4 Publication Policy

This study will be registered at ClinicalTrials.gov and after study completion, results information from this study will be posted to ClinicalTrials.gov. In addition, every attempt will be made to publish results in peer-reviewed journals. Publication of the results by the investigator will be subject to mutual written agreement between the investigator and the Sponsor or determined by the publication/steering committee prior to preparation of the publication.

# 15. APPENDICES

# Appendix 1 Cutaneous Reaction Assessment\*

Evaluate the tissue condition at the treatment site for the presence and severity of each of the following cutaneous reactions.

	Target Lesions		Nontarget Lesions		
Reaction	Lesion 1	Lesion 2	Lesion 1	Lesion 2	Lesion 3
Erythema	□ none	□ none	none	□ none	□ none
	□ mild	☐ mild	□ mild	☐ mild	☐ mild
	☐ moderate	☐ moderate	☐ moderate	☐ moderate	☐ moderate
	□ severe	severe	□ severe	□ severe	□ severe
Induration	none	□ none	none	□ none	□ none
	$\square$ mild	☐ mild	$\square$ mild	☐ mild	☐ mild
	☐ moderate	☐ moderate	$\square$ moderate	☐ moderate	☐ moderate
	□ severe	□ severe	□ severe	□ severe	□ severe
Swelling	none	□ none	none	□ none	□ none
	☐ mild	☐ mild	□ mild	☐ mild	☐ mild
	☐ moderate	☐ moderate	☐ moderate	☐ moderate	☐ moderate
	□ severe	□ severe	□ severe	□ severe	□ severe
Blister	□ none	□ none	□ none	□ none	□ none
Formation	□ mild	☐ mild	$\square$ mild	☐ mild	□ mild
	☐ moderate	☐ moderate	☐ moderate	☐ moderate	☐ moderate
	□ severe	□ severe	□ severe	□ severe	□ severe
Desquamation	□ none	□ none	□ none	□ none	□ none
	□ mild	☐ mild	$\square$ mild	☐ mild	□ mild
	☐ moderate	☐ moderate	☐ moderate	☐ moderate	☐ moderate
	□ severe	□ severe	□ severe	□ severe	□ severe

Evaluate the tissue condition at the treatment site for the presence and severity of each of the following cutaneous reactions.

	Target Lesions		Nontarget Lesions		
Reaction	Lesion 1	Lesion 2	Lesion 1	Lesion 2	Lesion 3
Erosion	□ none	□ none	□ none	□ none	□ none
	☐ mild	☐ mild	☐ mild	☐ mild	☐ mild
	☐ moderate	☐ moderate	☐ moderate	☐ moderate	☐ moderate
	□ severe	□ severe	□ severe	□ severe	□ severe
Ulceration	□ none	□ none	□ none	□ none	□ none
	☐ mild	☐ mild	☐ mild	☐ mild	□ mild
	☐ moderate	☐ moderate	☐ moderate	☐ moderate	☐ moderate
	□ severe	□ severe	□ severe	□ severe	□ severe
Necrosis	□ none	□ none	□ none	□ none	□ none
	☐ mild	☐ mild	☐ mild	☐ mild	☐ mild
	☐ moderate	☐ moderate	☐ moderate	☐ moderate	☐ moderate
	□ severe	□ severe	□ severe	□ severe	□ severe

\*Complete the assessment for each reaction and for any reaction that is Mild, Moderate or Severe enter event on the Adverse Event Page

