To gain additional information on the safety, tolerability and dosing regimen of VP-315 to support a pivotal study protocol design	
 
Treatment-related AEs; treatment-related serious adverse events (SAEs); discontinuations due to AEs; occurrence of TRAEs of special interest
 
CRA
 
	
Secondary Objectives	Endpoints	
To confirm the antitumor efficacy of VP- 315 using the optimal dosing regimen determined in Part 2	
 
Clinical clearance of treated lesion at excision as determined by visual assessment (no residual tumor seen on visual inspection)
 
Histological clearance of treated lesion(s) at excision
 
	
	Abscopal effect as determined by clinical and histological clearance of nontreated lesions at excision	
	
 
Estimate of remaining tumor volume (necrotic cells:tumor cells)
 
PGA
 
	
To characterize the pharmacokinetics (PK) of an 8 mg dose of VP-315 administered with the optimal dosing regimen	Plasma VP-315 concentrations	

Exploratory Objectives	Endpoints				
To assess subject and physician satisfaction with the treatment	
 
SCAR-Q, FACE-Q
 
Scar Cosmesis Assessment and Rating (SCAR) Scale
 
				
To assess the immune response to VP-315 treatment in a subset of subjects by assessing the immune repertoire in blood and in tissue	
 
Multiplex immunohistochemical staining for T-cell subsets and immune activation markers in tumor tissue samples
 
Analysis of T-cell clonality in blood and tumor tissue samples
 
				

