### 8.4.6 Cutaneous Reaction Assessment

A CRA will be performed prior to injection at all visits after W1D1 (Appendix 1); the evaluation results are required for the evaluation of necrosis and DLTs. These local skin reactions will be collected independently of the adverse reactions to provide information on the specific types of reactions that can be expected to occur.

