### 8.5 Pharmacodynamic Assessments and Endpoints

#### 8.5.1 Lesion Evaluation

At Screening, subjects will either provide a *HISTORICAL* biopsy (punch or shave) collected within the 90 days prior to the W1D1 visit or will undergo a punch or shave biopsy of the suspected BCC lesion within 90 days of W1D1. Shave biopsies will be performed according to standard of care and will include superficial or middle papillary dermis. For punch biopsies, a 2-mm punch biopsy will be collected for suspected BCC ≥0.5 cm to 1.0 cm, and a 3-mm punch biopsy will be collected for suspected BCC >1.0 cm to 2.0 cm, up to 5 suspected lesions may be biopsied. All specimens (including *HISTORICAL* samples) will be formalin-fixed and paraffin embedded (FFPE) and H&E stained slides of specimen slices will be prepared and reviewed locally to determine eligibility. The H&E stained slides will be sent to the central lab for imaging and high quality images of the slides will be sent to the central dermatopathologist for confirmation of analysis/histology.

In accordance with the procedures noted in Table 8-1, all target and nontarget BCC lesions will be surgically excised with a 3 mm- margin 4 to 6 weeks (Part 1) and 12 to 14 weeks (Part 2) after receipt of the W1D1 injection and tissue specimens preserved by FFPE. If a lesion has clinically cleared, the area where the lesion was will be excised accordingly. Both the screening and post-excision tissue blocks will be sent to the central lab for analysis of immune activation biomarkers including TILs by multiplexed IF-IHC, as well as for sequencing of genomic DNA from the lesion specimens to assess changes in T-cell receptor clonality.

During the study, subjects will be monitored for signs of efficacy—specifically, evidence of necrosis in the treated lesion(s).

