### **9.1. Adverse Events**

Adverse event (AE) summaries will be based on treatment-emergent adverse events (TEAEs). TEAEs are defined as AEs that started or worsened upon or after study treatment initiation. If it cannot be determined whether an AE is treatment emergent due to an incomplete or missing onset date and/or time, the AE will be considered treatment emergent. All AEs will be summarized using the safety population.

For AEs that are cutaneous injection site reactions (Erythema, Induration, Swelling, Blister Formation/Vesicles, Desquamation/Exfoliation, Erosion, Ulceration, Necrosis), severity was intended to be assessed on a cutaneous reaction assessment (CRA) grading scale (None (1), Mild (2), Moderate (3), Severe (4), Not Applicable (5)) and for all other AEs, severity was intended to be assessed according to the Common Terminology Criteria for Adverse Events (CTCAE) version 5.0 grading scale (Mild (1), Moderate (2), Severe (3), Life-threatening (4), Fatal (5)).

As the actual AE grading scale used was not captured in EDC, and the meaning of the grades is different across scales, the Maximum Severity and Grade  $\geq 2$  summaries will

be split into two sets, one for AEs that are cutaneous injection site reactions and one for AEs that are not cutaneous injection site reactions. For cutaneous injection site reactions, the preferred terms (PTs) that will be used are as follows: Injection site erythema, Injection site induration, Injection site swelling, Injection site vesicles, Injection site exfoliation, Injection site erosion, Injection site ulcer, Injection site necrosis.

An overall summary of adverse events will be provided where the number of TEAEs and the number and percent of each of the following items will be displayed.

- Subjects with at least one:
  - TEAE
  - TEAE by Strongest Relationship to Study Treatment (Not Related, Related)
  - TEAE Excluding Cutaneous Injection Site Reactions by Maximum Severity (Mild, Moderate, Severe, Life-threatening, Fatal)
  - TEAE of Only Cutaneous Injection Site Reactions by Maximum Severity (Mild, Moderate, Severe)
  - Grade  $\geq 2$  Events Excluding Cutaneous Injection Site Reactions:
    - TEAE
    - TEAE by Strongest Relationship to Study Treatment
    - TEAE Occurring upon Study Treatment through Observation Period (explained in detail below)
    - TEAE with Local Reactogenicity (Injection site pain)
    - TEAE with Systemic Reactogenicity (Fever, Myalgia, Headache)

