  - Severity  $\geq$  Moderate Events of Only Cutaneous Injection Site Reactions (excluding Severity = Not Applicable):
    - TEAE
    - TEAE by Strongest Relationship to Study Treatment
    - TEAE Occurring upon Study Treatment through Observation Period
    - TEAE with Local Reactogenicity (Injection site erythema, Injection site induration)
  - Serious TEAE
  - DLT - Part 1 Only
  - TRAE SI - Part 2 Only
  - TEAE Leading to Study Treatment Discontinuation

Verrica Pharmaceuticals Inc.  
Protocol: VP-315-201

Statistical Analysis Plan  
6-Sep-2024

- TEAE Leading to Study Discontinuation
- TEAE Leading to Death

Categories for Relationship to Study Treatment are Related and Not Related, and categories for Severity are Mild, Moderate, and Severe where the severe category will include severity levels of severe, life-threatening, and fatal as applicable.

Summaries of DLT events, TRAE SI events, and TEAEs for a subject Occurring upon Study Treatment through its Observation Period (e.g. during the DLT observation period or TRAE SI observation period) are TEAEs that a subject experiences on any day on which treatment occurs. This definition of the DLT and TRAE SI observation periods deviates from the protocol as described in section 14.

In addition, for each of the nineteen listed item mentioned previously in this section of the SAP, summaries for the total number of TEAEs, the number and percentage of subjects with at least one TEAE, and the number and percentage of subjects with at least one TEAE categorized by system organ class (SOC) and PT will be provided. Subjects having more than one AE may appear in more than one SOC or PT but will be counted at most once per each SOC and PT. For maximum severity, subjects will be counted at the most extreme category among the mild, moderate, and severe categories. For relationship to study treatment, subjects will be counted at the most related category among the unrelated and related categories. SOC and PT will be displayed in order of decreasing frequency of total SOC count, followed by decreasing frequency of total PT count, and then alphabetically if tied.

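### Target-lesion necrosis, the intended effect, counts in the all-grade related TEAE row, and no planned summary gives that row without it

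*Protocol*

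**What the plan says.** **Recording.** Protocol Appendix 1 has the site rate eight cutaneous reactions, necrosis among them, at each target and nontarget lesion. Its footnote adds: "for any reaction that is Mild, Moderate or Severe enter event on the Adverse Event Page". Protocol 8.4.6 describes the same reactions differently: "These local skin reactions will be collected independently of the adverse reactions".

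**Meaning of necrosis.** Protocol 8.5.1 says subjects are monitored for signs of efficacy, specifically "evidence of necrosis in the treated lesion(s". SAP 7.1.2 tabulates days to necrosis and total dose to necrosis.

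**Endpoints.** For Part 2, Protocol Section 3 lists treatment-related AEs as a primary endpoint, together with treatment-related SAEs, "discontinuations due to AEs; occurrence of TRAEs of special interest", and the CRA.

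**Analysis.** SAP 9.1 names the PTs that count as cutaneous injection site reactions; the list ends "Injection site exfoliation, Injection site erosion, Injection site ulcer, Injection site necrosis". It separates these PTs from other AEs only in the maximum-severity and Grade 2 or higher summaries, because the grading scale used was not captured. Two rows are not separated: "TEAE by Strongest Relationship to Study Treatment (Not Related, Related" and "TRAE SI - Part 2 Only".

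**The concern.** A row that reports a primary safety endpoint counts the effect the drug is meant to produce. A subject whose only related event is necrosis of the injected tumour appears as a subject with a treatment-related AE. Nothing in the summary tables tells that subject apart from one with pain, ulceration or a systemic reaction.

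The protocol's dosing rules keep the two ideas apart. In the Table 7-1 note for Cohorts 1 and 2, a TRAE and significant necrosis are alternative reasons to stop treating a lesion. A second lesion may follow necrosis provided no TRAE has occurred. If necrosis were itself a TRAE, that provision could never operate. The AE summary does not keep this distinction.

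At stake is how the related-AE rate is read when it supports the design of the pivotal study, which is the stated primary objective for Cohorts 4 and 5. A high rate could reflect poor tolerability or good activity.

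**Working it through.** **1. Does necrosis reach the row?** Appendix 1 sends mild or worse necrosis to the AE page with no exemption for target lesions. SAP 9.1 lists *Injection site necrosis* as an AE PT. The related row takes every TEAE judged related and has no exclusion. So necrosis enters whenever the site follows Appendix 1 and the investigator judges it related.

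**2. Is there a planned row without it?** SAP 9.1 says there are nineteen items. Counting them:

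- 4 all-grade items: any TEAE; TEAE by relationship; non-cutaneous by maximum severity; cutaneous by maximum severity
- 5 items for Grade 2 or higher, non-cutaneous
- 4 items for moderate or worse, cutaneous
- 6 others: serious, DLT, TRAE SI, treatment discontinuation, study discontinuation, death

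4 + 5 + 4 + 6 = 19, which agrees with the SAP.

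Six of these exclude cutaneous reactions. One is "TEAE Excluding Cutaneous Injection Site Reactions by Maximum Severity"; summing its categories gives subjects with any non-cutaneous TEAE, but for all causality. The other five are limited to Grade 2 or higher, one of them by relationship. None is both all-grade and related, and none excludes necrosis alone.

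**3. Can the count be derived from the SOC/PT tables?** Let R be the subjects in the related row, K those under related *Injection site necrosis*, and S those with a related TEAE other than necrosis. A subject may appear under several PTs, so the tables give only

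R − K ≤ S ≤ R.

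S is also at least as large as the biggest count under any other related PT. It is fixed exactly if K = 0, or if some other related PT already covers all R subjects.

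**4. How large could the difference be?** The documents give no event rates, so these inputs are assumptions. Let q be the share with related necrosis and r the share with any other related TEAE. Under independence the planned row reads 1 − (1 − q)(1 − r); a row without necrosis reads r. The excess is q(1 − r).

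| q | r = 30% | r = 50% | r = 70% |
|---|---|---|---|
| 50% | 65% (+35) | 75% (+25) | 85% (+15) |
| 70% | 79% (+49) | 85% (+35) | 91% (+21) |
| 90% | 93% (+63) | 95% (+45) | 97% (+27) |

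At r = 95% the excess is q × 5 points, that is 2.5 points at q = 50% and 4.5 at q = 90%. At r = 100% it is zero.

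Without independence the row lies between max(q, r) and min(1, q + r). At q = 50% and r = 70% that is 70% to 100%, so the excess runs from 0 to 30 points.

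**5. Effect on a comparison of two groups, same assumptions.** With equal r but necrosis in 50% of one group and 70% of the other, the row differs by (1 − r) × 20 points: 14, 8, 4 and 1 at r = 30%, 60%, 80% and 95%. Conversely, a true gap of 30% versus 50% in other related TEAEs shrinks to 20 × (1 − q) points: 15, 10, 5 and 2 at q = 25%, 50%, 75% and 90%.

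**The case against.** The strongest reply is that this is a display preference in a descriptive study with no formal inference.

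- **Necrosis is already visible.** SAP 9.5 tabulates it by lesion and visit, SAP 7.1.2 gives days and dose to necrosis, and the SOC/PT table for related TEAEs shows its count.
- **The count can be recovered.** SAP 9.1 plans a subject-level AE listing with event, TEAE status, severity and relatedness. A reader might infer that the number is lost. It is not; it can be read by hand. What is missing is a pre-specified summary.
- **The illustration depends on its inputs.** Appendix 1 also makes mild erythema, swelling and induration into AEs, and reports of injection-site pain prompted an ad hoc SRC meeting. If nearly every subject has one of these, removing necrosis changes almost nothing. Independence is also doubtful for reactions at the same lesion.
- **The PT is not purely efficacy.** Appendix 1 rates tissue at the treatment site, so the term can include necrosis of surrounding skin.
- **The two recording texts may be compatible.** Protocol 8.4.6 can mean a separate CRA form kept alongside AE entry. That is a fair reading, and the point does not rest on a contradiction.

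All of this stands, and it limits the size of the point. It does not supply the missing row.

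Two stronger readings are tempting, and the documents do not support them.

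The first is that the TRAE SI row is also mixed with necrosis. Protocol 10.2 would admit any related Grade 2 or higher AE, with no exclusion for necrosis. But SAP 4.1 takes TRAE SI status from EDC, and nothing shows that sites flagged necrosis. The protocol points the other way: 10.2 ends dosing after a TRAE SI, while Cohorts 4 and 5 are dosed for their fixed days whatever the necrosis status.

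The second is that Cohort 5's third treatment day lets more necrosis into its TRAE SI window than Cohort 4's. That longer window applies to every kind of AE, so it is not an argument about necrosis.

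**Conclusion.** The point holds for the all-grade related TEAE row. Necrosis of the treated lesion is the named sign of efficacy, it is entered as an AE, and it counts in a row that reports a Part 2 primary endpoint. No planned summary table gives the subject count without it, or without the eight cutaneous PTs. For the TRAE SI row the problem is only possible.

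The size is unknown. Under the assumed rates above the row could be inflated by 15 to 63 points. It could equally be inflated by almost nothing if other related local reactions are close to universal. The conclusion assumes that sites followed Appendix 1 and that investigators judged necrosis related. It is a worthwhile, low-cost improvement to the plan, not an error that invalidates the safety analysis.

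**What to change.** Before database lock, keep all existing rows and add to SAP 9.1 two subject-level rows, each with its SOC/PT table and shown for the groups in SAP 5.5:

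- (a) all-grade related TEAEs excluding the PT *Injection site necrosis*
- (b) all-grade related TEAEs excluding all eight cutaneous PTs, to match the split the SAP already uses

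Row (a) answers the question directly. It keeps injection-site erythema and induration, which Protocol 10.2 names as toxicity; row (b) drops them. Add a TRAE SI row excluding necrosis only if any necrosis event is flagged as a TRAE SI in EDC.

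The cost is a few extra tables built from PTs the SAP already lists, with no new data and no protocol amendment. Because the PT cannot separate tumour necrosis from necrosis of surrounding skin, the existing row must stay beside the new ones. If the database is already locked, the rows can still be produced, but SAP 5.2 would require them to be labelled post hoc.
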